## 10.2 Statistical Analysis

Acceptability, the primary outcome, will be assessed through tabulation of survey results and in-depth interviews. We will use a threshold of  $\geq 75\%$  reporting that the full PrEP-BAY intervention was at least somewhat acceptable on a 5-point Likert scale, and then explore potential mechanisms through in-depth interviews using a sequential explanatory mixed methods approach. For the interviews, we will analyze transcripts using the codebook and theoretical model developed in Aim 2, applying it to a subset of transcripts. We will seek 90% agreement among coders prior to applying codes to the entire set of interviews. We will use code reports to organize findings into emergent themes and discuss these as a group and with the HIV prevention community advisory group.

Preliminary impact (adherence) will be assessed via a long-term adherence metric, namely DBS TFV-DP levels. We will use mixed effects logistic regression for high adherence (at least 4 times weekly dosing; TFV-DP  $\geq 700$  fmol/punch) comparing the interaction of adherence by intervention arm with time. Random intercepts will accommodate paired adherence levels. As an additional adherence outcome, we will examine continuous DBS TFV-DP levels using censored mixed-effects linear regression in a similar fashion.

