	independent DSMB. Serious adverse events will be monitored by the committee on an ongoing basis throughout the study.
STATISTICS Primary Analysis Plan	
Acceptability will be the primary outcome for this pilot randomized controlled trial, and will be assessed via tabulation of survey results with graded answers in the intervention arm. Frequency distributions of the Likert scale will be summarized. Advantages and disadvantages of the bioassay enhanced brief adherence intervention will be tabulated, including manually reviewing and assigning open-ended responses under the “other” option to appropriate pre-specified categories. We will use a threshold of <math>\geq 75\%</math> reporting that they were at least somewhat satisfied with the full PrEP2-BAY intervention.
 
After analysis of the quantitative results, we will explore mechanisms of acceptability using a sequential explanatory mixed methods approach. Qualitative interviews from the participants and providers will be performed, a debrief report will be prepared, and audio recordings will be professionally transcribed. Coding and analysis will be performed in the Dedoose cloud-based analysis platform to facilitate collaboration and comparison of coding transcripts. At least 10% of transcripts will be double-coded and compared among the analytic team and inter-coder agreement will be calculated. Inconsistent results will be reviewed by coders until consensus on codes and themes is reached.
 
Preliminary impact on adherence as assessed by hair tenofovir levels (long-term adherence): The first adherence analysis will include use of a mixed effects logistic regression model to estimate the effect of the intervention vs. SoC arm on optimal vs. sub-optimal adherence (<math>< 700</math> fmol/punch) equivalent to at least 4-times weekly average dosing over the prior three months. We will include a random intercept term to account for within-person correlation over two timepoints; and time points will be included as a categorical variable to account for systematic changes over time. We will also analyze continuous tenofovir-diphosphate levels between intervention and SoC arms using a censored-mixed effects linear regression with logarithmically transformed levels of tenofovir in hair.

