#### 5.2 Secondary Endpoint

Preliminary impact on adherence as assessed by tenofovir hair levels (long-term adherence): Change in tenofovir levels in hair from baseline and after 3 months of follow-up will be compared between the intervention and standard of care arm.

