### 9.2 Hair Sample Collection

Prior to the Month 0 visit, hair collection instructions will be sent to the participant. Instructions will be provided and will be reviewed with the participant at the Month 0 visit. All participants will self-collect (at home) hair samples using a pair of scissors at study enrollment and at three months and will place them in a pre-addressed and prepaid envelope to be sent back to the UCSF HAL. Approximately 50 strands of hair will be collected (less than is lost from the scalp in a day). Home collected hair specimens will be used for measurement of tenofovir, a marker of long-term adherence to PrEP. Participants will send the hair sample via the mail to the UCSF Hair Analytic Lab for analysis. No other analyses will be performed on this sample and it will be destroyed after analysis.

	Screening/ Enrollment	Month 0	Month 3
Assess eligibility	√		
Informed consent	√		
Randomization	√		

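### Section 10.2 builds both adherence models on a dried-blood-spot measure that the trial does not collect, and the binary model has no usable cut-off for hair

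*Combined protocol and SAP*

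**What the plan says.** **Section 10.2 (Statistical Analysis)** names the outcome: "Preliminary impact (adherence) will be assessed via a long-term adherence metric, namely DBS TFV-DP levels". High adherence is TFV-DP of at least 700 "fmol/punch) comparing the interaction of adherence by intervention arm with time", fitted by mixed-effects logistic regression. For the second model, "we will examine continuous DBS TFV-DP levels using censored mixed-effects linear regression in a similar fashion".

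**Synopsis, Statistics row**, has a hair heading, "Preliminary impact on adherence as assessed by hair tenofovir levels (long-term adherence"), but its logistic model uses a cut-off of 700 "fmol/punch) equivalent to at least 4-times weekly average dosing over the prior three months". Its continuous-model sentence begins "We will also analyze continuous tenofovir-diphosphate levels between intervention and SoC arms" and ends by specifying a censored mixed linear model on log-transformed tenofovir in hair.

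**Section 5.2 (Secondary Endpoint)**: "Change in tenofovir levels in hair from baseline and after 3 months of follow-up will be compared" between arms.

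**Section 9.2 (Hair Sample Collection)**: "Home collected hair specimens will be used for measurement of tenofovir, a marker of long-term adherence to PrEP". It adds that the sample will have no other analysis and will then be destroyed.

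**The concern.** The analysis section and the measurement sections describe different specimens. TFV-DP per blood-spot punch and tenofovir in hair differ in matrix, analyte and unit, so one cannot stand in for the other, and a threshold for the first cannot classify the second.

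Three things are at stake.

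- Adherence impact is the only secondary endpoint. The Synopsis also places it inside its primary objective, and the findings are meant to support a larger grant application.
- The Synopsis lists the logistic model as the first adherence analysis, and that is the model without a usable outcome definition.
- The trial is open-label. An interim analysis of all data is planned when about half of participants have finished, and the board's report (section 11.3) includes secondary outcomes by group. If a hair cut-off has to be found after such data exist, the binary result is open to the charge that the cut-off was chosen to suit them.

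**Working it through.** No sample size, power or event count enters this point, so there is no stated figure to reproduce. The check sets the sections side by side.

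| Place | Specimen and analyte | Cut-off |
|---|---|---|
| 3.2 Secondary Objectives | Hair, tenofovir | none |
| 4.1 Study Overview | Hair, tenofovir, baseline to month 3 | none |
| 5.2 Secondary Endpoint | Hair, tenofovir, change compared between arms | none needed |
| 6.1 Study Population | Participants give urine and hair | n/a |
| 9.2 and the schedule | Hair tenofovir, both arms, months 0 and 3 | none |
| 9.3 and the schedule | Point-of-care urine, intervention arm only | adherent or non-adherent by the assay |
| 12 Laboratory Specimens | Hair only | n/a |
| Synopsis, logistic model | Hair heading, per-punch unit | 700 fmol/punch |
| Synopsis, continuous model | TFV-DP and log hair tenofovir in one sentence | none |
| 10.2, logistic model | DBS TFV-DP | 700 fmol/punch |
| 10.2, continuous model | DBS TFV-DP | none |

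1. **Is blood collected anywhere?** No section provides for collecting, shipping or assaying blood or blood spots. The risk section (9.8) covers urine and hair collection and mentions no blood sampling. DBS TFV-DP will therefore be available for 0 of 60 participants.

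2. **Could TFV-DP come from the hair sample?** No. Section 9.2 has the hair assayed for tenofovir and rules out any other analysis.

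3. **Could urine substitute?** No. It is collected only in the 40 intervention participants, so it gives no comparison with the 20 controls.

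4. **Can the 700 figure be carried over to hair?** No. Section 10.2 ties it to DBS TFV-DP. The documents give no conversion to a hair concentration and no hair cut-off for at least 4 doses per week.

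5. **Is this only loose terminology?** The Background treats hair and dried blood spots as separate matrices and cites TFV-DP as a DBS measure, so the authors distinguish the two.

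6. **Count of model statements that can be run.**
   - Section 10.2: 0 of 2.
   - Synopsis: 1 of 2. The logistic model has no usable cut-off; the continuous model works if the hair half of its sentence governs.
   - Together: 0 + 1 = 1 of 4, and that one depends on choosing between two analytes named in the same sentence.

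7. **What is not touched.** The primary endpoint is satisfaction in the 40 intervention participants. The sample-size statement rests on it alone (75% threshold, 90% assumed).

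**The case against.** The strongest reply is that the intent is plain. The objective, overview, endpoint, collection procedure, schedule and laboratory section all say hair; only the Statistics row of the Synopsis and section 10.2 depart from it. On that view this is a wording slip in a secondary, preliminary analysis of a 60-person pilot. Much of this stands for the continuous model: the Synopsis already names log hair tenofovir, and correcting the analyte settles the matter. It does not stand for the binary model. Changing the analyte there leaves no cut-off at all, and the documents supply none.

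The documents do not support three stronger readings that a reader might infer.

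- *That hair is the only specimen.* Urine is also collected in the intervention arm. The accurate statement is that no dried blood spots are collected.
- *That no planned adherence model can be run, leaving the secondary endpoint without a valid analysis.* The endpoint in section 5.2 is change in hair tenofovir, which needs no cut-off, and the Synopsis names a model that can estimate it. The dichotomised outcome is not itself a listed endpoint.
- *That analysts will apply 700 to hair values or choose a cut-off after seeing results.* Neither is planned anywhere. The plan leaves that door open, which is a risk and not a stated intention.

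**Conclusion.** The point holds within limits. Both models in section 10.2 name an analyte that will be measured in none of the 60 participants. The logistic model lacks a valid cut-off in section 10.2 and in the Synopsis alike. The continuous model is wrong in 10.2 and self-contradictory, but recoverable, in the Synopsis. The text specifies an analysis and a threshold that do not fit the data, which is more than missing detail, so it needs correcting before adherence data are analysed. The effect is confined to the secondary adherence analysis; acceptability and the sample size are not affected.

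This rests on the documents as they stand: that no blood-spot collection is arranged outside them, and that no hair cut-off is fixed in a document not included here.

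**What to change.** In the Statistics row of the Synopsis and in section 10.2:

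- Replace DBS TFV-DP with hair tenofovir concentration. State the laboratory's unit and the assay lower limit at which values will be censored; the censored model cannot be specified without that limit.
- Analyse the stated secondary endpoint, change in hair tenofovir, with the censored mixed model on log hair tenofovir.
- Keep the binary model only if a justified hair cut-off for at least 4 doses per week is fixed before any outcome data are seen, including data prepared for the interim review. It would then replace 700 fmol/punch. Otherwise delete the binary model and every reference to 700 fmol/punch.

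In the same edit, make the two places agree on the effect tested: section 10.2 describes an arm-by-time interaction, while the Synopsis describes an arm effect with categorical time.

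The cost is protocol and SAP wording plus an enquiry to the hair laboratory about unit, lower limit and any cut-off. No new samples, visits or participants are needed. The documents do not show that the laboratory holds a suitable cut-off, so the binary analysis may be lost.

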## 10.3 Qualitative Data analysis

Recordings of the in-depth interviews (IDIs) will be analyzed using software for qualitative analysis. Interviewers will complete a debrief report promptly following each interview to capture results relevant to the study objectives. Debrief reports will also include an assessment of whether the interview merits additional in-depth analysis. Debriefing reports have been shown to be of sufficiently high quality to use as a primary source. Debrief reports and selected transcripts will be reviewed for emergent themes and results relevant to the study objectives. Team members will create summary reports based on this analysis for use in providing feedback and suggestions in achieving study goals, and to contribute to manuscript development. Debrief reports will be reviewed promptly in order to provide feedback and suggestions for subsequent interviews..

## **11. Safety Monitoring and Clinical Data Review**

### **11.1. Safety Monitoring and Clinical Data Review**

A multi-tiered safety review process will be followed for the duration of this study. Close cooperation between the PI, investigators, study coordinator, statistician, and other study team members will be necessary to monitor participant safety and to respond to occurrences of toxicity in a timely manner. The research team will have regularly scheduled meetings during the period of study implementation, and additional ad hoc calls will be convened if required.

### **11.2 Reporting Requirements for this Study**

This study will follow safety reporting requirements as outlined by the UCSF IRB. All adverse events that are definitely, probably, or possibly related, AND serious or unexpected, will be reported to the IRB within 5 working days of PI awareness. All AEs meeting these criteria will be reported to the study PI within 48 hours of site awareness, to allow ample time for IRB notification. The NIH Project Officer will be provided copies of these reports at the time of IRB reporting and informed of any actions taken by the IRB as a result of such events.

Serious adverse events are any AEs that result in any of the following outcomes:

- Death,
- Life-threatening adverse experience,
- Inpatient hospitalization or prolongation of existing hospitalization,
- Persistent or significant disability/incapacity,
- Congenital anomaly/birth defect, or cancer, or
- Any other experience that suggests a significant hazard, contraindication, side effect or precaution that may require medical or surgical intervention to prevent one of the outcomes listed above

Unexpected AEs are those that exceed the nature, severity or frequency described in the current IRB Application including the protocol, consent form and investigator brochure (when applicable). An unexpected AE also includes any AE that meets any of the following criteria:

- Results in subject withdrawal from study participation,
- Due to an overdose of study medication, or
- Due to a deviation from the IRB approved study protocol

In addition, all SAEs will be reported to the study team within 72 hours of recognition by study staff.

### **11.3 Data Safety Monitoring Board (DSMB)**

We will form a dedicated DSMB for PrEP2-BAY. Membership will include a researcher with experience in conducting trials to address PrEP uptake and persistence; a clinician with expertise in HIV treatment and prevention, including PrEP adherence measures; a biostatistician with expertise in PrEP intervention trials; and a community member.

The purpose of the DSMB will be:

- To ensure the safety of trial participants
- To preserve validity and integrity of research data
- To facilitate the availability of timely as well as reliable findings to the broader clinical community

The DSMB will meet by teleconference every 6 months, and more frequently as needed. No DSMB members will be permitted to have any financial interest related to the outcome of the trial. Individuals on the DSMB will be required to disclose in writing to the NIH project officer of any potential conflicts of interest, actual or implied.

The DSMB will review the PrEP2-BAY protocol prior to launch of the trial, and monitor follow-up to identify unexpected events that change the known risks to participation. The DSMB may make recommendations to continue, modify, or terminate the trial based on their findings. Recommendations will be made in writing to the PI and the NIMH Program Officer.

The DSMB report will contain a brief description of the trial, baseline socio-demographic characteristics of participants (total and by group), status of recruitment, retention, and disposition of study participants (total and by group), description of any quality assurance or regulatory issues, a report of AEs and SAEs (including social harms) (total and by study group), and the status of outcome data. Protocol compliance will be evaluated by reviewing: the expected recruitment rate, study drop-outs and reasons for leaving the study, data quality assurance reports, overall data flow procedures, questionnaires completed and CRFs entered; protocol deviations; protocol violations; missing data; staff omissions; subject refusal to provide data. The outcome data report will include outcome data analyzed by group, with calculation of p-values at the direction of the DSMB, and include all primary and secondary outcome variables.

### **11.4 Social Impact Reporting**

Although the study site will make every effort to protect participant privacy and confidentiality, it is possible that participants' involvement in the study could become known to others, and that a negative social impact may result (e.g. participants could be perceived as being HIV-infected or at "high risk" for HIV infection). For example, participants could be treated unfairly, or could have problems being accepted by their families and/or communities. In the event that a participant reports a negative social impact, every effort will be made by study staff to provide appropriate care and counseling to the participant as necessary, and/or referral to appropriate resources for the safety of the participant. Staff will provide such care and counseling in accordance with standardized guidance.

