STUDY DESIGN	This is a randomized, unblinded, open-label pilot study

PRIMARY OBJECTIVE	To test the acceptability to participants and impact on a longer-term metric of adherence among participants (assessed via tenofovir levels in hair) of implementing POC urine tenofovir testing and providing adherence feedback and motivational interview-based counseling among YMSM in the U.S.
NUMBER OF SUBJECTS	60 participants, 40 in the intervention arm and 20 in the standard-of-care arm
SUBJECT SELECTION CRITERIA	
Inclusion Criteria:
 
 
1. Age 18-30 years.
 
2. Primary sexual partners are male sex at birth
 
3. Able to understand, read, and speak English.
 
4. Currently taking TDF/FTC-based, daily PrEP and planning to continue for at least 3 months
 
5. Willing to provide a hair sample
 
 
Exclusion Criteria:
 
 
1. Any health condition that may interfere with participation or the ability to provide informed consent, including any debilitating or life-threatening conditions
 
2. Currently enrolled in another HIV intervention study.
 
3. Known to be HIV-infected.
 

POC TESTING	Urine tenofovir testing by lateral flow assay performed at each of 2 counseling sessions approximately 2-3 months apart
CONTROL	Participants will continue to receive standard of care at their PrEP clinic without the PrEP2-BAY adherence counseling intervention
DURATION OF SUBJECT PARTICIPATION AND DURATION OF STUDY	Participants will be enrolled in the study for a maximum of 3 months, including the enrollment period and 3 months of study follow-up.
PRIMARY ENDPOINT	
 
• Acceptability: Number of participants indicating satisfied or very satisfied with the intervention
 
• Description: Number of participants reporting to be "satisfied" or "very satisfied" about their overall experience on a five-point Likert scale.
 
• Time Frame: 3 months
 

SECONDARY ENDPOINTS	
 
• Change in tenofovir levels in hair from baseline and after 3 months of follow-up
 

PLANNED INTERIM ANALYSES	When approximately 50% of patients have completed all study procedures, an interim analysis of all data will be conducted by an

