### 9.3 Urine Sample Collection and Analysis (Intervention Arm Only)

Prior to the Month 0 visit, urine test kits will be sent to all participants in the intervention arm. Urine samples will be collected by the participant before or during the video visit only for participants in the intervention arm. Urine is collected with a volume of at least 5mL into a

urine collection cup provided to the participant. The urine may be collected at the beginning of the urine stream (no need for clean catch). The participant will be provided instructions on how to complete the urine test, and may discuss any questions with the research coordinator at the time of enrollment/first study visit

The participant will be provided a \$50 cash or gift card reimbursement for completion of all study procedures at each visit, including the survey and urine collection. Reimbursement may be provided via an e-gift card or check.

Hair TFV Levels		√	√
POC Urine Testing (intervention arm only)		√	√
PrEP2-BAY Counseling Intervention (intervention arm only)		√	√
Online questionnaire		√	√

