#### **9.6 In-depth Interviews**

In-depth interviews will be conducted among 20 YMSM to assess acceptability, as well as to explore mechanisms by which the intervention motivated changes in adherence. We will use purposive sampling among participants in the intervention arm, with a goal to include 15 individuals who reported adherence challenges and 5 who did not report adherence challenges, as well as achieve a racially/ethnically and geographically diverse sample of respondents. Participants will receive an additional \$50 reimbursement for completing an interview.

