#### **9.8 Risks to Participants**

There is potential for loss of confidentiality in all research, but risk to participants will be minimized by training all staff in the ethical conduct of research. Data for the participants in this study will be obtained from the medical record, or from behavioral questionnaires administered (via tablet or personal electronic device).

If data related to illicit drug use were disclosed due to a loss of confidentiality, there could be risk of criminal justice involvement.

There is no substantial risk for urine collection or performance of the urine point of care test.

Participants may feel slight pulling at the scalp when using scissors to collect a hair sample.

Participants will be asked questions about their sexual behavior that may make them feel uneasy. Participants do not have to answer any question that they do not want to and can stop answering the questions at any time. Participants may also become embarrassed, worried, or anxious when being counseled about PrEP.

Strict protection of the data will be maintained through using password protected databases. There may be risks of discrimination or other personal problems from being in this study. The most common risks we know about are family or friends worrying, getting upset or angry, or assuming that you are HIV-infected and treating you unfairly as a result. The study staff will take the same steps to protect participant privacy. The participant may be embarrassed or feel uncomfortable with some of the questions that are asked during the study. The participant does not have to answer any questions that make them uncomfortable.

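### No structured elicitation of adverse events or social harms is described in either arm, so the by-arm counts promised to the DSMB may not be comparable

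*Combined protocol and SAP*

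**What the plan says.** Section 9.8 expects harms that are mainly social and psychological: "There may be risks of discrimination or other personal problems from being in this study". It also names unfair treatment by family or friends, unease or anxiety during PrEP counseling, and legal exposure if drug-use data were disclosed.

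Section 11.3 lists among the contents of the DSMB report "a report of AEs and SAEs (including social harms) (total and by study group"), and allows the DSMB to recommend continuing, modifying or terminating the trial.

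On how such events come to light, the protocol says little:

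- Section 11.4: "In the event that a participant reports a negative social impact, every effort will be made by study staff" to provide care, counseling or referral.
- Section 11.2: the AE clock starts at site awareness and the SAE clock at recognition by study staff.
- Schedule of procedures (rows under Sections 9.2 and 9.3): eligibility, consent, randomization, hair levels, urine test, counseling and online questionnaire. No readable row covers AEs or social harms.

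Contact with staff differs by arm. The counseling row reads "PrEP2-BAY Counseling Intervention (intervention arm only") and is ticked at Month 0 and Month 3. For the 20 in-depth interviews, Section 9.6 states: "We will use purposive sampling among participants in the intervention arm". Common to both arms are two video or phone visits for each of the 60 participants (Section 9.1) and a questionnaire of about 100 questions after each visit (Section 9.5; its schedule row has no arm restriction).

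**The concern.** A by-arm harms table can be read as a comparison only if both arms were asked in the same way. Here every trigger described is passive, and one arm has more opportunity for a harm to come up in conversation. The two counseling sessions deal with adherence and with substance use and HIV risk, subjects on which a participant might well mention a family conflict or an unwanted disclosure. Standard-of-care participants have study assessments only.

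An excess in the intervention arm could then be real harm, better detection, or both. A zero in the standard-of-care arm could mean no harm, or no occasion to mention one. The DSMB would have no means of telling these apart, and analysts cannot recover the information once data collection is over.

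**Working it through.** The plan states no harm rate, capture rate or sample size for harms, so there is no figure of its own to reproduce. The check counts contacts and then shows how far unequal contact could move the counts.

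**Inputs from the protocol.** Arm sizes: "60 participants, 40 in the intervention arm and 20 in the standard-of-care arm" (Synopsis). Research visits: 2 per participant in both arms (Section 9.1). Questionnaires: 2 per participant in both arms (Section 9.5). Counseling sessions: 2, intervention arm only (Section 9.4). Interviews: 20, intervention arm only (Section 9.6), an average of 20/40 = 0.5 per intervention participant.

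**Step 1: contacts per participant.**

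| Way of counting | Intervention | Standard of care | Ratio |
|---|---|---|---|
| Visits only | 2 | 2 | 1.00 |
| Visits and interviews, counseling inside visits | 2 + 0.5 = 2.5 | 2 | 1.25 |
| The same, plus questionnaires | 4.5 | 4 | 1.13 |
| Visits and interviews, counseling counted separately | 2 + 2 + 0.5 = 4.5 | 2 | 2.25 |
| The same, plus questionnaires | 6.5 | 4 | 1.63 |

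The schedule puts counseling in the same Month 0 and Month 3 columns as the other visit procedures, so the rows with counseling inside visits fit the documents better.

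**Step 2: effect on captured harms.** Let q be an assumed chance that a harm is mentioned at any one contact, and k the number of contacts. Then P(captured) = 1 − (1 − q)^k. Questionnaires are left out, since no harm item is described. Standard of care has k = 2. In the intervention arm, half have k = 2 and half k = 3 (counseling inside visits), or half k = 4 and half k = 5 (separate). True harm rates are set equal.

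For q = 0.2:

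- Standard of care: 1 − 0.8² = 0.360.
- Intervention, inside visits: 0.5 × 0.360 + 0.5 × 0.488 = 0.424; ratio 0.424/0.360 = 1.18.
- Intervention, separate: 0.5 × 0.590 + 0.5 × 0.672 = 0.631; ratio 0.631/0.360 = 1.75.

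| q (assumed) | Ratio, inside visits | Ratio, separate |
|---|---|---|
| 0.05 | 1.23 | 2.11 |
| 0.2 | 1.18 | 1.75 |
| 0.5 | 1.08 | 1.27 |
| 0.8 | 1.02 | 1.04 |

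The model gives every contact the same q. If a counseling conversation draws out more than an ordinary visit does, the inside-visits column is too low.

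**Step 3: expected counts.** With an assumed true harm rate of 10% in both arms, true events are 20 × 0.10 = 2 in standard of care and 40 × 0.10 = 4 in intervention. At q = 0.2, captured events are 2 × 0.360 = 0.7 against 4 × 0.424 = 1.7 or 4 × 0.631 = 2.5. The chance of no recorded event in standard of care is (1 − 0.10 × 0.360)^20 = 0.964^20 = 0.48. With complete capture it is 0.90^20 = 0.12.

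**Step 4: with identical solicited items.** Each arm has k = 2 solicited occasions, so the ratio of captured harms on those items is 1.00 at any q common to both arms.

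**The case against.** Four arguments on the other side have weight.

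First, a reader might infer that harms are captured only if a participant volunteers them. The documents do not establish this. The questionnaire items, case report forms and counseling manual are not reproduced, and Section 9.8 names the medical record as a further data source. What stands is narrower: no elicitation is described, although a by-arm report depends on it. The record is also a weak substitute. Section 9 describes no retrieval of it, PrEP care takes place outside the study (Section 7), and family rejection or discrimination would seldom be entered there.

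Second, a reader might infer that the intervention arm has many more separate occasions to report. It does not, on the natural reading of the schedule: counseling falls at the same time points as the visits both arms attend. The difference is more conversation at those visits, plus one interview for half of the arm.

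Third, a reader might infer that harm reporting closes before the interviews, because the Synopsis says "Participants will be enrolled in the study for a maximum of 3 months" and also "After analysis of the quantitative results, we will explore mechanisms of acceptability using a sequential explanatory mixed methods approach". No section closes a reporting window. The clocks in Section 11.2 run from awareness, so a harm disclosed at interview is not excluded.

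Fourth, this is a pilot in 60 people with no harms hypothesis. The DSMB sees much else besides this table, and IRB reporting depends on relatedness and on seriousness or unexpectedness, not on an arm contrast. With so few events, chance would probably outweigh a modest detection difference. All of that limits the importance of the point. It does not remove it, since the protocol itself promises the by-group split.

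**Conclusion.** The point holds in a limited form. The protocol describes no structured, arm-neutral elicitation of AEs or social harms, and the intervention arm has more staff conversation, so the by-group counts may not be comparable. The likely direction is more complete detection in the intervention arm. The size is unknown: the illustration gives apparent ratios of 1.02 to 1.23 with counseling inside the visits and 1.04 to 2.11 with it counted separately, all resting on assumed values of q and equal true rates.

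It would go too far to say that the table is biased, or that any excess is a detection artefact. Section 9.8 recognises that counseling may cause embarrassment or anxiety, and only the intervention arm receives study counseling, so part of an excess could be real. The primary acceptability endpoint and the hair-level endpoint are unaffected. This is an inexpensive improvement that has to be made before data collection. If the questionnaire already contains such items, a sentence saying so and a schedule entry would settle most of it.

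**What to change.** 1. Unless they are already there, add a few identical yes/no items to the online questionnaire in both arms, at Month 3 and, as a baseline, at Month 0. Cover the harms named in Section 9.8 (unfair treatment or discrimination, problems with family or friends, unwanted disclosure, distress from study procedures) plus hospitalisation. State the recall period, because Section 9.5 places the questionnaire after each visit and so after the first counseling session.
2. Ask about distress from counseling in the intervention arm only, and show it separately.
3. Continue to report all AEs and SAEs by group as Section 11.3 promises, including those reported spontaneously. Record the source of each event: solicited item, visit, counseling, interview or spontaneous report.
4. Use the solicited items for the like-for-like arm comparison, and flag events learned only through counseling or interviews.
5. Add one row to the schedule and one line to the DSMB report shell.

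Cost: about 5 items on a questionnaire of about 100 that takes 20 to 30 minutes. Pro rata that is 5/100 × 20 to 30 = 1 to 1.5 minutes, so one to two minutes each time, plus more minor events to log. One limit remains: the trial is open-label (Section 8.2), so asking equally does not guarantee that participants answer equally.
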